1 STUDY SCHEDULE OF ACTIVITIES

The Schedule of Activities table provides an overview of the protocol visits and procedures. Refer to the Study Conduct Section (6) for detailed information on each procedure and assessment required for compliance with the protocol.

Table 1 Study Schedule

Schedule of Events

| PHASE | SCREENING PHASE | | Dosing | TREATMENT PHASE | | FOLLOW-UP PHASE |
|------------------------------|----------------------------|------------------|--------|---------------------------------------------------------------------------|---------------------------------------------|-----------------|
| | Screening/ Presentation | Pre -First dose* | | Every 6 hours post first dose until discharge or as indicated (+/-1 hour) | Every 24 hours post first dose (+/-2 hours) | |
| Informed consent | X | | | | | |
| History | X | | | | | |
| Physical/ Review of Systems | X | X | | | X | X |
| Vital Signs | X | X | X | | | X |
| CBC, Differential, Platelets | X | X | X | | | |
| Transaminases (AST, ALT) | X | X | X | | | X |
| ALP | X | X | X | | | X |
| Ammonia | X | X | X | | X | X |
| Lactate | X | X | X | | | |
| Amylase | X | X | X | | | X |
| Lipase | X | X | X | | | X |
| Bilirubin (total) | X | X | X | | X | X |
| PT | X | X | X | | X | X |

| PHASE | SCREENING PHASE | | TREATMENT PHASE | | | FOLLOW-UP PHASE |
|--------------------------------------------------------------------------------------------------------------------------|----------------------------|------------------|-----------------|---------------------------------------------------------------------------|---------------------------------------------|-------------------------------------------------------------|
| | Screening/ Presentation | Pre -First dose* | Dosing | Every 6 hours post first dose until discharge or as indicated (+/-1 hour) | Every 24 hours post first dose (+/-2 hours) | |
| Event | | | | | | At Follow-up, 10 (+/- 2) Days after study drug discontinued |
| INR | X | X | | X | | X |
| BUN, Creatinine, GFR | X | X | | X | X | |
| Glucose | X | X | | X** | X | |
| Electrolytes (NA, K, Cl, CO2) | X | X | | X | | |
| Serum Pregnancy test for woman of child bearing potential | X | | | | | |
| Loading dose Legalon-SIL 5mg/kg IV over 1 hour followed by continuous IV infusion of 20 mg silibinin/kg over 24 hours | | | X | | | |
| Adverse Events | X | X | X | X | X | X |
| Concomitant Medications | X | X | X | X | X | X |

¹ * All labs to be repeated if first dose occurs greater than 4 hours from last set of labs.

² ** If subject is diabetic, then follow institution's standard for glycemic monitoring.

2 INTRODUCTION

2.1 Indication

Ingestion of amatoxin containing mushrooms may account for approximately 95% of deaths attributable to mushroom ingestion worldwide. In the United States, European invader *Amanita phalloides* and California native *Amanita ocreata* account for almost all cases reported on the West Coast (during the rainy season from September to April). *Amanita bisporigera* and *Amanita virosa* are responsible for poisonings in the Midwest and East Coast (April to September).

Amanita mushrooms are often mistaken for nonpoisonous species, even by experienced mushroom foragers, particularly immigrants familiar with similarly appearing mushrooms in their home environment. They are often described as delicious (“best tasting mushrooms I have ever eaten”) and the onset of initial GI symptoms can be delayed by six or more hours.

The principal toxins (amanitins) are not destroyed by cooking, freezing, or drying, however, the mushrooms themselves are completely safe to handle (1). Amanitins are processed via enterohepatic circulation, are secreted in the bile, taken up by hepatocytes and tightly bound to RNA polymerase II, suppressing protein synthesis and resulting in severe acute hepatitis and fulminant hepatic failure. It is believed that prevention of the secretion of the toxin from the bile, by either gall bladder drainage or inhibition of gall bladder contractility, may help to mitigate the magnitude of the amanitins’ toxicity.

2.2 Background and Rationale

The use of Legalon® SIL (silibinin) for amatoxin poisoning has a well-recognized biochemical mechanism of action: inhibition of OATP1B3 mediated amanitin uptake by hepatocytes (3, 4). This data also suggests that Penicillin G works by the same mechanism, although with a much less significant effect, and that combining Penicillin G with silibinin may lead to a reduced therapeutic effect. The undesirability of combining Penicillin G with silibinin was the subject of a paper published in Germany which suggested less favorable outcomes when Penicillin G combination therapy was used in comparison to silibinin monotherapy (5).

A second mechanism of action Legalon® SIL has also emerged. Amatoxin appears to induce fulminant hepatic failure via TNF mediated hepatocyte apoptosis. Building on earlier work it now appears that silibinin may inhibit TNF release in the injured liver (6, 7, 8, 9).

Legalon® SIL reduced death in amatoxin-poisoned dogs from 80% to 0% (10). This is the only substance that has been shown to be of benefit for post exposure prophylaxis against fulminant hepatic failure and death in this species.

Although there are no controlled studies of Legalon® SIL for amatoxin poisoning, open-label treatment in Europe compared to historical controls, suggests that mortality is markedly decreased from 22% to 10% among all subjects treated with Legalon® SIL (11, 12).

Diagnosis

Amatoxin poisoning is diagnosed by the clinical history and laboratory findings, specifically:

- a. History of eating foraged mushrooms

- b. Gastrointestinal symptoms consistent with amatoxin poisoning (cramping abdominal pain, nausea, vomiting, and / or watery diarrhea) usually 24-48 hours after mushroom ingestion
- c. Liver function tests consistent with amatoxin poisoning: AST or ALT above the upper limit of normal after mushroom ingestion

Amatoxin Poisoning Clinical Picture and Laboratory Findings

Amatoxin Poisoning Clinical Picture and Laboratory Findings

Patients who consume amatoxin containing mushrooms exhibit signs and symptoms that typically occur in a progression through three stages.

Stage I:

There is an initial quiescent period (6-24 hours post ingestion) after which cramping abdominal pain, nausea, vomiting, and watery "cholera like" diarrhea develop. Routine laboratory values may reflect dehydration and electrolyte loss, but they may not accurately assess the magnitude of intoxication or predict the eventual outcome.

Stage II

The second stage of amatoxin poisoning is characterized by generalized clinical improvement (resolution of gastrointestinal symptoms) that begins 24 to 48 hrs after ingestion, albeit masking the hepatic deterioration that is occurring at the same time. The liver function tests show a progressive elevation of transaminases and an evolving coagulopathy. Early renal damage may be reflected by elevations in the serum creatinine and blood urea nitrogen levels.

Grade 1: Patients develop gastroenteritis-like symptoms several hours (6-36) after ingestion but do not develop severe biochemical indications of hepatitis (peak transaminases <1000 without coagulopathy) or renal dysfunction.

Grade 2: In addition to GI symptoms patients manifest a moderate (1000-5000 IU/L) rise in transaminases and a moderate (peak INR <2.0) coagulopathy.

Stage III

Transition into the third stage can occur quite suddenly. Hepatic failure may be fulminant and is manifested by a severe increase in serum transaminases and profound coagulopathy. Patients may experience a swift progression from Stage I to Stage III or IV. The presence of hypoglycemia is a poor prognostic sign reflecting massive hepatic necrosis. Normalization of transaminases in the setting of a rising INR, creatinine, ammonia level plus worsening symptoms, should be considered to be a sign of fulminant hepatic necrosis and, hence an indicator of poor prognosis. Renal failure, due to hepatorenal syndrome and/or direct nephrotoxicity of amanitins, may result in severe oliguria or anuria. Fifty percent of patients with amatoxin poisoning may also have laboratory evidence of pancreatitis (2).

Grade 3: Patients develop a marked elevation of transaminases (>5000 IU/L) and significant coagulopathy (INR>2.0). Grade 3 is divided into two subgroups according to bilirubin values. In Grade 3a: hyperbilirubinemia is mild or absent, while Grade 3b: shows a steep and continuous rise in bilirubin (greater than 5 mg/dL).

Grade 4: A steep rise in transaminases is accompanied by a corresponding steep decline in clotting function (INR>3.0) and renal dysfunction.

Grade 1 and Grade 2 patients have the best chance of surviving amatoxin poisoning and need symptomatic treatment only. Grade 3, particularly Grade 3b patients, are at risk and should be

transferred to a tertiary care center where liver transplant is available. Grade 4 patients have an extremely poor prognosis. There is a 90% probability of death in spite of intensive therapy. Survival usually requires a liver transplant.

Laboratory Abnormalities and Corresponding Prognostic Indication

Transaminases

Grade 1 patients show mild elevations of liver enzymes. Grade 2 patients develop a moderate rise in transaminases, usually below 5,000 IU/L but sometimes much higher. Grade 3 patients show a steep and massive rise in transaminases. There is no significant difference in the magnitude of transaminase results in Grade 4 relative to Grade 3, although in fatal cases the mean values are generally higher. A decrease of transaminase values on Day 4 is either a sign of improvement or a hepatic "burn-out" phenomenon. A massive rise in transaminases (Grade 3 and 4) does not necessarily predict a fatal outcome, whereas a mild rise in transaminases (Grade 2) generally indicates a good chance for survival.

Prothrombin Time

PT/INR is of high prognostic value. An early and steep prolongation of prothrombin time values suggests a poor prognosis. In Europe, those patients in whom prothrombin times could not be improved to values above 20-30% by substitution of clotting factors on Days 3-4 had >90% mortality. From 48 hrs after ingestion onwards, there is a significant difference between the prothrombin time of survivors in Grade 3 (>30 %) and non-survivors in Grade 4 (< 20%).

Bilirubin

On admission to the hospital, bilirubin values are normal in 90% of all cases. Elevation at this early stage (>3 mg/dL) suggests a poor prognosis. During the course of the intoxication, only about 20% of Grade 3 patients (Grade 3b) show a marked rise in bilirubin. It is possible to obtain information on the prognosis from the absolute values after Day 3. At that time, values < 5 mg/dL indicate a favorable prognosis, even if transaminases are high, while a value > 5 mg/dL indicates a severe or fatal course.

Impairment in kidney function

Early renal dysfunction signals a poor prognosis. Prerenal azotemia secondary to dehydration on initial presentation is a common finding that can usually be reversed by aggressive fluid replacement. Acute tubular necrosis may also occur in severely dehydrated patients and may represent a direct cytotoxic effect of amatoxin. A slight elevation of creatinine on Days 1 to 2 that does not respond to fluid replacement suggests that a direct toxic effect has occurred. About 70% of fatal cases show this early increase of creatinine. Hepatorenal syndrome occurs later and indicates an extremely poor prognosis.

In summary, Legalon® SIL will be administered to patients with amatoxin poisoning diagnosed by history, gastrointestinal symptoms, elevated liver enzymes. Treatment will consist of a 5 mg/kg loading dose followed by 20 mg/kg/day via continuous infusion (13). The treating physician is expected to administer supportive therapy of his/her choosing but consistent with best practices. Legalon® SIL will be discontinued when coagulopathy is no longer present, and when liver function tests have returned to no greater than 2 times the upper limit of normal or patient does not respond to treatment with Legalon® SIL. Patients will be followed 10 (+/-2) days after the end of Legalon® SIL therapy with follow-up laboratory studies and physical exam. If the Follow-up Visit is not feasible due to patient's

condition, reason for the missed visit must be clearly documented in the patient's medical record.

Complete information for Legalon® SIL may be found in the Legalon® SIL Investigator's Brochure.

2.2.1 Rationale for Dose Selection

A study was conducted aiming at the verification of Legalon® SIL reconstituted solution in infusion bags containing 5% glucose solution. The stability was tested up to 30 hours at 25°C/60% RH.

The design of the study was as follows:

- 4 times 35 ml were taken from a 500 ml Glucose (5%) infusion bag
- 4 vials of Legalon SIL were reconstituted with 35 ml each
- after reconstitution the 4 solutions were returned into the infusion bag
- the infusion bag (containing 4 vials of Legalon SIL) was stored under defined conditions for min. 24 hrs. (study report number 02VB0164_07/01).

This kind of preparation was intended to be used for a 24 hrs. infusion.

A stability of the solution of minimum 30 hrs. could be confirmed.

Based on the results, it was concluded that, the reconstituted solution of Legalon® SIL is stable at 25°C/60% RH, as shown by content of Silibinin mono- and dihydrogensuccinate (SHS), sodium salts.

Although there was a slight increase of the content of SHS, sodium salts, from 1.8% to 3.0% of batch number 120204 1nd from 1.3% to 2.4% of batch no. 163601 the values were still far below the specification limit of not more than 5.5%.

Therefore, the study verifies that the reconstituted solution of Legalon® SIL is from the analytical point of view stable at 25°C/60% RH for 24 hours.

No microbiological investigations were performed in this study, because such aspect depends more on the GCP application than on the product itself, which is sterile and is to be dissolved in sterile media.

3 OBJECTIVES AND ENDPOINTS

3.1 Objectives

3.1.1 Primary objective

The primary objective is to evaluate the efficacy of Legalon® SIL in preventing hepatic failure and/or death resulting from amatoxin poisoning in a phase II clinical trial

3.2 Endpoints

3.2.1 Primary Endpoints

The primary endpoint is the proportion of subjects treated with Legalon® SIL that do not exhibit morbidity (liver transplantation and/or mortality (death)).

3.2.1.1 Safety

Safety based on the evaluation of changes in baseline laboratory and clinical presentation while on study treatment. The laboratory values to be followed are transaminases and renal function tests (AST, ALT, bilirubin, PT/INR, creatinine, lactic acid).

3.2.2 Secondary Efficacy

Efficacy as demonstrated by time to normality of the laboratory values from start of treatment with Legalon® SIL. The laboratory values to be followed are transaminases and renal function tests (AST, ALT, bilirubin, PT/INR, creatinine, lactic acid).

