| | 
approximation, a sample size of 139, provides a two-sided 95% confidence interval for proportion of subjects not meeting the outcome of interest (liver transplantation and/or death) within a half width of 5% from the observed proportion at an expected proportion of 90%.
 |
| 
Statistical Methods
 | 
Demographic and Anamnestical Data:
 
All demographic and anamnestical data will be analyzed descriptively. For quantitative variables, the descriptive summary (means, medians, standard deviation, minimum and maximum) will be calculated. For qualitative data, the corresponding absolute and relative frequencies will be determined.
 
Efficacy Analysis:
 
The primary endpoint is the proportion of subjects treated with Legalon[®] SIL that do not exhibit morbidity (liver transplantation) and/or mortality (death).
 
Proportion of subjects not meeting outcome of interest (liver transplantation and/or death) will be determined. Furthermore, the corresponding 95% confidence intervals will be determined.
 
Sensitivity Analyses:
 
Subject survival rate without hepatic transplantation and/or death will be calculated for all subjects and for each stage of disease. Moreover, the corresponding 95% confidence intervals for the rate of survival will be determined. The survival time will be described by means of Kaplan-Meier estimates.
 
Secondary endpoint (efficacy):
 
 • All quantitative secondary endpoints will be analyzed descriptively. Means, medians, standard deviations, minimum and maximum will be calculated as measures of location and dispersion. • The time to normality for AST, ALT, bilirubin, PT/INR, and creatinine, if abnormal at presentation, will be determined for all subjects and for each stage of disease by means of Kaplan-Meier estimates. 
Additional summaries -- Assessment of Emergency Liver Transplantation Criteria in ALF due to Amanita Poisoning – using Ganzert’s and Escudie’s criteria. (13a.
 
 • Number (%) of subjects without hepatic transplantation by Ganzert’s intoxication (pre-treatment) • Elapsed days between amanita poisoning and start of treatment |

| | |

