7.4 Secondary Endpoint (s)

The secondary endpoints of the study are:

- Proportion of patients not needing liver transplantation
- The time to normality for AST, ALT, bilirubin, PT/INR, and creatinine during the treatment period
- Number (%) of patients without hepatic transplantation by Ganzert's intoxication (pre-treatment)
- Elapsed days between amanita poisoning and start of treatment
- Number (%) of patients without hepatic transplantation by Ganzert's intoxication (during treatment)
- Number (%) of patients without hepatic transplantation by INR severity criteria (INR < 2 and ≥ 2) (during treatment)
- Number (%) of patients without hepatic transplantation by Escudie's intoxicion grade transplantation criteria (INR < 6 and ≥ 6) (during treatment)

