7.5.7 Analysis of Secondary Endpoint(s)

All secondary analysis will be carried out using the Full Analysis Set.

The endpoints of proportion of patients not needing liver transplantation, without hepatic transplantation by Ganzert's intoxication (pre-treatment), without hepatic transplantation by Ganzert's intoxication (during treatment), without hepatic transplantation by INR severity criteria (INR < 2 and ≥ 2) (during treatment), without hepatic transplantation by Escudié's intoxication grade transplantation criteria (INR < 6 and ≥ 6) (during treatment) will be analyzed in the same way as the analysis of primary endpoint. The number and proportion of patients meeting the criteria will be computed and presented along with 95% CI that is computed using Newcombe-Wilson score method.

Elapsed days between amanita poisoning and start of treatment will be summarized descriptively.

The time to normality for AST, ALT, bilirubin, PT/INR, and creatinine will be analyzed using Kaplan-Meier estimation method of estimation for the survival time. 95% CI will be computed for the survival rate by using Greenwoods formula. The analysis of time to normality for AST, ALT, bilirubin, PT/INR, and creatinine will be analyzed by the disease severity stages as well.

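### Time to laboratory normality is timed from first dose in an uncontrolled trial, so its curve mixes any drug effect with delay since ingestion

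*Combined protocol and SAP*

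**What the plan says.** Section 3.2.2 sets both the purpose and the clock: "Efficacy as demonstrated by time to normality of the laboratory values from start of treatment with Legalon® SIL". Section 7.4 restricts the window: "The time to normality for AST, ALT, bilirubin, PT/INR, and creatinine during the treatment period". Section 7.5.7 gives the method: "The time to normality for AST, ALT, bilirubin, PT/INR, and creatinine will be analyzed using Kaplan-Meier estimation method of estimation for the survival time". It adds Greenwood intervals and says that the endpoint "will be analyzed by the disease severity stages as well". The synopsis adds an at-risk rule for each test: "if abnormal at presentation, will be determined for all subjects and for each stage of disease by means of Kaplan-Meier estimates".

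The delay from ingestion to treatment is itself a listed secondary endpoint in Section 7.4 ("Elapsed days between amanita poisoning and start of treatment"), but Section 7.5.7 stops there: "Elapsed days between amanita poisoning and start of treatment will be summarized descriptively". Nothing makes delay a stratum, covariate or entry time for time to normality.

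Section 2.2 times the illness from ingestion. There is a silent period of 6 to 24 h, then a second stage "that begins 24 to 48 hrs after ingestion" during which liver tests are still worsening. Prothrombin time separates survivors from non-survivors from 48 h, and a possible turn in transaminases is placed at Day 4. Section 4.3.4 withdraws patients whose laboratory values show recovery before the first dose. Section 4.3.3 confirms that there is no randomisation.

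**The concern.** Two patients with the same illness and the same calendar of recovery get different values of this endpoint if one receives the drug a day later. The later patient has less of the course left to run, and is in the data only if not yet recovered. The clock therefore credits part of the elapsed illness to the treatment.

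With a concurrent control arm this would largely cancel. Here there is none, so the curve itself is the evidence, and Section 3.2.2 presents it as showing efficacy. A summary that depends on how quickly patients were referred, approved by an IRB and supplied with drug (Section 6.1) cannot be read as a drug effect. It also cannot safely be compared with another series that had different delays. By-stage curves have the same weakness if the stages differ in delay.

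**Working it through.** **The plan's own figure.** The documents state no figure for this endpoint. The sample size reproduces (1.96² × 0.90 × 0.10 / 0.05² = 138.3, rounded up to 139), but it concerns the primary proportion only.

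**Inputs from the documents.**
- Time origin at first dose (3.2.2); Kaplan-Meier with no delayed entry (7.5.7).
- Starts within 48 h and beyond 48 h are described in the published experience under 7.1. Starts beyond 96 h occurred in this trial (7.6). Section 4.3 sets no upper limit on time since ingestion.
- Patients already recovering are removed before dosing (4.3.4).

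**Assumptions.** The documents give no time from ingestion to normal values. I assume medians of 120, 168 and 240 h, a lognormal shape with log-SD 0.35, an inert drug, and recovery time unrelated to delay. The last two isolate the effect of the clock; they do not describe the trial.

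**Formula.** Let T be time from ingestion to normality with survival function S, and d the delay to first dose. The first-dose clock records T − d among patients with T > d.
- Apparent median = S⁻¹(S(d)/2) − d.
- Share normal within 96 h of first dose = 1 − S(d + 96)/S(d).

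**Worked case, median 168 h (7 days).**
- d = 48 h: S(48) ≈ 0.9998. S falls to half of this at 168.0 h, and 168.0 − 48 = 120 h, or 5.0 days.
- d = 72 h: S(72) = 1 − Φ(ln(72/168)/0.35) = 1 − Φ(−2.42) ≈ 0.992. S falls to 0.496 at about 168.6 h, and 168.6 − 72 ≈ 97 h, or 4.0 days.

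**Range over the assumed median** (apparent median in hours; in brackets, % normal within 96 h of first dose):

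| Assumed median from ingestion | Start 24 h | Start 48 h | Start 72 h | Start 96 h |
|---|---|---|---|---|
| 120 h | 96 (50%) | 72 (70%) | 52 (82%) | 39 (88%) |
| 168 h | 144 (17%) | 120 (33%) | 97 (50%) | 76 (63%) |
| 240 h | 216 (2%) | 192 (7%) | 168 (15%) | 144 (26%) |

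Moving the start from 48 h to 72 h shortens the apparent median by 20, 23 or 24 h (28%, 19% or 12.5%) with no drug effect at all.

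**Shape.** At a median of 168 h, lognormal log-SDs of 0.2 and 0.5 give 120 and 121 h for a 48 h start, against 96 and 101 h for a 72 h start. Weibull shapes 2 and 3 give 127 and 121 h against 111 and 100 h. Only a constant hazard removes the shift (168 h at every start). That fits poorly with tests that first worsen for days, as Section 2.2 describes.

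**Is the time origin the cause?** In simulated trials of 139 patients under the 168 h model, starts at 36 h and 72 h gave first-dose medians of about 133 and 97 h. With the clock at ingestion and entry at first dose, both were 169 h. The 36 h gap equals the difference in delay (72 − 36).

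**The case against.** The strongest reply is that the model leaves out what the trial has already seen. The literature summary under 7.1 says that delay beyond 48 h made a severe course more likely. Section 7.6 reports that everyone who started after 96 h had a negative outcome. A reader might infer from the table that late-treated patients will appear to recover faster. The documents do not support that: greater severity among late starters pushes the other way and could cancel or reverse the clock effect. This part of the reply stands. What remains is that delay and severity are both mixed into the curve.

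Other points that stand, in whole or part:
- **Window.** Section 7.4 confines the endpoint to the treatment period, which Section 7.3 puts at 96 h (the synopsis allows longer). With a 96 h cut-off, a median of 5.0 days would not be reached. The bias then shows in the height of the curve: 33% against 50% normal by 96 h for starts at 48 and 72 h under the 168 h assumption.
- **Stages.** One might argue that a later stage means a later start, so the by-stage curves are the worst affected. Section 2.2 gives both stages loosely timed from ingestion and grades defined by laboratory peaks, and it notes swift progression between stages. Section 7.5.7 does not say which it means, and it plans no test between stages. The link is plausible but not established.
- **Time zero.** First dose is a conventional origin. A delayed-entry analysis from ingestion needs entry time to be independent of prognosis, which Sections 7.1 and 7.6 put in doubt. It is not a clean replacement.
- **Importance.** The endpoint is descriptive and one of seven in Section 7.4. Section 7.5 leaves detailed methods to a SAP that is not reproduced here, so some of this may be settled there.

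**Conclusion.** The concern holds as a problem of interpretation. An uncontrolled time-to-normality curve from first dose combines any drug effect, referral delay and severity, and the current plan does nothing to separate them. Under an inert drug and equal severity, a 24 h later start takes about a day off the apparent time (20 to 24 h over the assumed range). This size rests on assumed recovery times; the sign rests on a recovery hazard that rises with time since ingestion.

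The net direction in the trial's data is unknown. The more dramatic contrast between starts at 24 h and 96 h, which roughly halves the median at 168 h, should not be relied on: the documents do not show that starts at 24 h occur, and nobody in the interim report who started after 96 h did well. The primary endpoint and N = 139 are untouched. This is an inexpensive improvement to a secondary analysis, not a flaw in the trial's main result.

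**What to change.** In Section 7.5.7 (and the SAP):

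1. Keep first dose as time zero, but present time to normality within bands of ingestion-to-first-dose time: up to 48 h, over 48 to 96 h, and over 96 h. These splits come from the narrative under 7.1 and from 7.6; they are not existing analysis strata.
2. Count death and liver transplant as competing events and report cumulative incidence of normalisation. The plan does not say how they are handled. Censoring them would drop the worst cases from the risk set (8 of the first 50 patients in Section 7.6).
3. State that the overall and by-stage curves will not be read as evidence of drug effect without the delay bands.
4. Optionally, add an ingestion-origin Kaplan-Meier with delayed entry at first dose as a sensitivity analysis, stating its assumption that entry time is independent of prognosis.

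**Cost.** A little programming and SAP text. Section 7.5 lets the SAP modify protocol plans and asks for an amendment only for major changes to the primary endpoint. No visit, sample or treatment changes.

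**Downsides.**
- Bands will be small. At the interim, all who started after 96 h were among the 8 negative outcomes, so that band held at most 8 of 50 patients and may yield no normalisations.
- Ingestion time is patient-reported, and the endpoint is listed in days, so delay must be recorded finely enough to apply the 48 h and 96 h cut-offs.
- Bands reduce the mixing but do not remove it. Under the 168 h model, apparent medians still run from 120 h to 76 h across the middle band.
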